2.1 Rationale

Based on the promising results that genotyping-based strategies for warfarin has shown thus far, a rational approach would be to investigate the possibility of reducing the complexity of the genotyping procedures so as to cut-down the turn around time required for identifying the various genetic variants of CYP2C9 and VKORC1. Timely implementation of a genotype-guided dosing approach in the clinical setting would be required to maximize the potential clinical benefits. In addition, simplified sequencing and genotyping of both CYP2C9 and VKORC1 would pose to be more cost-effective for routine screening in clinical practice.

2.2 Hypothesis and study objectives

We hypothesize that warfarin dose requirement could be more accurately predicted using a simplified genotyping procedure requiring the identification of a single CYP2C9 allele and a single nucleotide polymorphism of VKORC1.

The primary objective is to assess the clinical benefits of genotype-guided dosing of warfarin against the traditional mode of dosing which uses only clinical factors.

The secondary objective is to prospectively evaluate the accuracy and precision of the pharmacogenetic dose-prediction model used to calculate the maintenance dose for patients in the pharmacogenetics arm.

3. Patient Selection

3.1 Eligibility Criteria

- 1. At least 18 years of age
- 2. New indication for warfarin therapy
- 3. No previous history of liver disease; transaminases must be less than 3 times upper limit of normal and bilirubin within normal range

Protocol No: PG01/11/06 Version 13, 24 April 2014

- 4. No previous history of malabsorption syndrome or chronic diarrheal conditions
- 5. Written, informed consent

3.2 Exclusion Criteria

- 1. Uncontrolled hypertension
- 2. Peptic ulcer disease
- 3. Any other medical conditions as deemed unfit for warfarin therapy based on clinical judgement of primary physician

4. Investigational Plan

4.2 Study Design

Study endpoints and Statistical Considerations Refer to Appendix 4 – Statistical Analysis Plan

Accrual of study subjects with new indication for warfarin therapy (n = 350)

Informed consent

Patient Randomization; Determination of target therapeutic INR

Traditional dosing regimen

Pharmacogenetics-guided dosing

Dose Initiation Regimen (first 3 days)			
	Traditional dosing regimenPharmacogenetics-guided dosing		
Day 1	Low-molecular weight heparin	Low-molecular weight heparin	
Day 2	Low-molecular weight heparin	Low-molecular weight heparin	
Day 3	Low-molecular weight heparin Warfarin 5mg	Low-molecular weight heparin Warfarin tailored dose (if pharmacogenetics results available)	
Day 4	Low-molecular weight heparin Warfarin 4mg if age >75 years All others 5mg	Low-molecular weight heparin Warfarin tailored dose (if pharmacogenetics results available)	
Day 5	Low-molecular weight heparin Warfarin 3mg	Low-molecular weight heparin Warfarin tailored dose (if pharmacogenetics results available) Switch to standard protocol if pharmacogenetics results not available by day 5	
Day 6	Low-molecular weight heparin Check INR Warfarin dose according to Appendix 1A For all subsequent INRs checked during dose initiation phase, Warfarin dose will be determined by Appendix 1B	Low-molecular weight heparin Warfarin tailored dose (if pharmacogenetics results available) Check INR if three doses of warfarin had been administered, and dose subsequent warfarin dose according to Appendix 2A. For all subsequent INRs checked during dose initiation phase, Warfarin dose will be determined by Appendix 2B	
7-9 days after initiation of warfarin	INR check	INR check	
12-14 days after initiation of warfarin	INR check	INR check	

* Once therapeutic INR is achieved, low-molecular heparin should be stopped, and INR should be re-checked at least once within a week (this may coincide with the INR check on day 7-9 or day 12-14)

Maintenance Dose Regimen

- Once INR is maintained within the target range of 2-3 for 2 or more consecutive checks without a change in dose for at least 3 months, patients are considered to have reached maintenance dose.
- The total period of follow up for this study is approximately 3 months
- The number and frequency of visits should be between 3 to 5 during the first 2 weeks of initiating therapy although more visits may be required depending on the individual patient's response to warfarin therapy.

4.3 Patient data collection

Baseline characteristics will be obtained from all patients accrued into the study. These include race, age, sex, weight, height, liver and renal function, and concomitant medications. The INR values and dates of tests for each patient will also be recorded, together with any tests of the prothrombin time (PT), partial thromboplastin time (PTT). Each adjustment in warfarin dose will also be recorded and the corresponding INR checked within 1 week. Patients potentially eligible for this study will be screened from both the inpatient and outpatient services. INR will be performed using the standard venous blood sample.

[figure not shown]
4.4 Derivation of Warfarin Dosing Model with Validation

A total of 220 complete datasets were available for constructing the warfarin dose requirement linear regression model. Demographic predictors used for model-building included age, weight, sex, ethnic group (Chinese, Malay, Indian, Others), serum albumin concentration, INR and the presence of CYP2C9*3 variant and VKOR-381 CC genotypes. Log-transformation was applied to warfarin doses to achieve normality in its distribution. Univariate anaylses were conducted to retain the closely associated predictors for further model building. Only those variables with p < 0.1 in the initial analysis were considered as sufficiently associated with warfarin dose and retained for further model-building. Only those predictors showing statistical significance of p < 0.05 and did not demonstrate collinearity were retained in the final model. A data-splitting method that randomly assigned approximately 50% of the available dataset for model building and the remaining half for model validation was employed.

One hundred and eleven patients were randomly selected into the model-building dataset and the remaining 109 formed the validation cohort. The initial multiple linear regression model using the logarithmic derivation of warfarin dose featured the patient age, body weight, Indian and Chinese ethnic groups as well as the pharmacogenetic predictors *VKORC1-381* CC, *VKORC1-381* TC, *CYP2C9*2* and *CYP2C9*3* as predictors. It exhibited an r^2 of 0.609. Collinearity checks of the model showed tolerance values of between 0.287 for *VKORC1-381* CC genotype to 0.898 for age, and corresponding VIF values of 3.49 to 1.114. However, the p values of the 2 ethnic group and *CYP2C9*2* predictors did not reach statistical significance (p>0.05). Hence, they were removed from the final regression model. Details of the final linear model are available on request. Standardized residuals were between -2.9 to 2.0. Overall, this model showed only a very slight compromise in correlation (0.78 to 0.77) when compared to the initial model and still explained for 59.2% of the variation in warfarin dose. Data from remaining subjects (n = 109) were used to validate this derived model. It showed an overall under-prediction of 0.37 \pm 1.26 mg/day, ranging from -5.1 to 2.4 mg/day.

Figure 1. Difference in warfarin dose against average of actual and estimated doses, with 95% limits if agreement (broken line) and regression line (solid line). Subjects with *VKORC1-381* CC genotype are marked by the open circles, TC genotype by solid triangles and TT genotypes by open squares. ($r^2 = 0.346$)

Predicted minus actual dose (mg/day)

4.5 Warfarin Administration

All predicted warfarin dose will be administered by rounding down to the nearest 0.5 mg. Warfarin (Marevan®) is available as 1mg (brown), 3 mg (blue) and 5 mg (pink) oral tablets from GlaxoSmithKline Pte. Ltd. Patients and/or their caregivers will be given dietary advice upon initiation of warfarin therapy to avoid drug-food interactions affecting warfarin pharmacokinetics.

Suitable alternatives of warfarin or generic drugs may be used instead.

4.6 Genotyping

Details of genotyping were described in our previous papers for CYP2C9 and VKORC1 respectively.^{8,26} Genotyping tests for CYP2C9 will be reduced to a single variant, testing only for CYP2C9*3 and VKORC1 to one SNP -381. Samples consisting of 10 mls of blood will be drawn from patients once written, informed consent is given. All samples will be labeled and coded in identification numbers to ensure patient confidentiality.

4.7 Safety

Investigators are responsible for monitoring the safety of subjects who have entered this study and for alerting the Principal Investigator of any event that seems unusual, even if this event may be considered an unanticipated benefit to the subject.

The investigator is responsible for appropriate medical care of subjects during the study.

The investigator remains responsible for following, through an appropriate health care option, adverse events that are serious or that caused the subject to discontinue before completing the study. The subject should be followed until the event resolves or is explained. Frequency of follow-up is left to the discretion of the investigator.

4.8 Potential Risks

Patients in the pharmacogenetics-guided dosing group in this study should not be subjected to any potential risks greater than those in the traditional dosing cohort or not participating. INR will be checked within 3 to 5 days of the first dose of warfarin and within 1 week for every dose adjustment. The dose will be immediately adjusted according to Appendices 1 (for traditional arm dosing) and 2 (for pharmacogenetics arm dosing) if any deviation from the target INR is observed. The only risks involved in this study are the blood draws, which carry a very small risk of local pain, bleeding and infection. However, as the blood draw for the pharmacokinetics study will be done at the same time as the routine laboratory tests (eg INR) after the patient has reached a stable INR, the patients are not put at any higher risk than those not participating.

4.9 Safety Measures

Safety measures that will be used in the study include physical examinations and clinical laboratory tests (haematology and blood chemistries).

4.9.1 Safety Reporting to DSRB and HSA

An adverse event is any untoward medical occurrence in a clinical investigation patient administered a pharmaceutical product and which does not necessarily have to have a causal relationship with this treatment. A Serious Adverse Event is any untoward medical occurrence at any dose that:

- 1. Results in death or;
- 2. Is life-threatening or;
- 3. Requires inpatient hospitalization or prolongation of existing hospitalization or;
- 4. Results in persistent or significant disability/incapacity or;

- 5. Is a congenital anomaly/birth defect;
- 6. Is a medically important event.

All SAEs that are unexpected and related to the study drug will be reported. The investigator is responsible for informing HSA no later than 15 calendar days after first knowledge that the case qualifies for expedited reporting. Follow-up information will be actively sought and submitted as it becomes available. For fatal or life-threatening cases, HSA will be notified as soon as possible but no later than 7 calendar days after first knowledge that a case qualifies, followed by a complete report within 8 additional calendar days.

4.10 Potential Benefits

Patients will not get any monetary gains from this study. In the event that a blood test needs to be repeated, patients will receive transport reimbursement.

Appendix 1A

INR	Warfarin Dose	LMWH	Remarks
<1.5	4mg	Continue	Recheck INR in 1-3 days ^c
1.51-3	3mg	Stop if INR > 2	Recheck INR within 1 week ^c
3.01-	2mg	Stop	Recheck INR within 1 week ^c
3.5			
>3.5	Omit	Stop	Recheck INR in 1-3 days ^c

Appendix 1B

INR	Actions	
<1.5	Increase warfarin dose by 25% (round down to nearest 0.5mg).	
	Re-check INR the next day	
1.51-3	Maintain same warfarin dose	
3.01-3.5	Reduce warfarin dose by 25% (round down to nearest 0.5mg)	
3.51-4	Reduce warfarin dose by 50% (round down to the nearest 0.5mg)	
	Re-check INR the next day	
>4	Omit dose for the day. Re-check INR the next day	

	Warfarin Dose	LMWH	Remarks
Appendix			
2AINR			
<1.5	Increase warfarin	Continue	Recheck INR in 1-3 days ^c and refer to
	dose by 25%		Appendix 2B for subsequent dosing.
	(round down to		
	nearest 0.5mg).		
1.51-3	Maintain same	Stop if	Recheck INR within 1 week ^c and refer to
	warfarin dose	INR > 2	Appendix 2B for subsequent dosing.
3.01-3.5	Reduce warfarin	Stop	Recheck INR within1 week ^c and refer to
	dose by 25%		Appendix 2B for subsequent dosing.
	(round down to		
	nearest 0.5mg)		
>3.5	Omit dose for the	Stop	Recheck INR in 1-3 days ^c and restart
	day		warfarin at 75% of original dose (ie. reduce
			warfarin dose by 25 % rounded down to
			nearest 0.5mg). Refer to Appendix 2B for
			subsequent dosing

Appendix 2B

INR	Actions	
<1.5	Increase warfarin dose by 25% (round down to nearest 0.5mg).	
	Re-check INR the next day	
1.51-3	Maintain same warfarin dose	
3.01-3.5	Reduce warfarin dose by 25% (round down to nearest 0.5mg)	
3.51-4	Reduce warfarin dose by 50% (round down to the nearest 0.5mg)	
	Re-check INR the next day	
>4	Omit dose for the day. Re-check INR the next day	

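### In Appendices 1B, 2A and 2B the 25% increase for INR below 1.5 leaves 0.5, 1.0 and 1.5 mg unchanged, so during initiation these doses can fall but not rise

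*SAP*

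**What the plan says.** Section 4.2 (Study Design) assigns the dosing tables. In the pharmacogenetics arm the first INR is handled by Appendix 2A and later INRs in the initiation phase by Appendix 2B. In the traditional arm the first INR is handled by Appendix 1A, which sets fixed doses of 4, 3 or 2 mg or an omission, and later ones by Appendix 1B.

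The rows that matter are these:

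- INR below 1.5 (1B, 2A, 2B): "Increase warfarin dose by 25% (round down to nearest 0.5mg".
- INR 1.51 to 3 (1B, 2A, 2B): "Maintain same warfarin dose".
- INR 3.01 to 3.5 (1B, 2A, 2B): "Reduce warfarin dose by 25% (round down to nearest 0.5mg".
- INR 3.51 to 4 (1B, 2B): "Reduce warfarin dose by 50% (round down to the nearest 0.5mg".
- INR above 3.5 (2A only): omit a dose, then restart "warfarin at 75% of original dose (ie. reduce" by 25%, with the same rounding.

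None of these tables states a minimum step. Section 4.5 also rounds the predicted dose down to a 0.5 mg multiple and sets no floor. Section 4.8 relies on these appendices to correct INR values that leave the target. Appendix 3 raises the dose by a fixed 1 mg for INR below 1.5, but its title restricts it to the maintenance phase.

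**The concern.** A row that orders an increase should produce one. At low doses a quarter of the dose is less than one 0.5 mg step, and rounding down removes it. The tables already have a separate row for holding the dose, so an unchanged dose is not what the row for INR below 1.5 intends. The reductions use the same rounding, and there it makes the cut larger.

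At stake is whether the tables can correct a subtherapeutic INR in a patient on a small dose. As written, a prescriber who follows them exactly re-checks the INR and leaves the dose where it was.

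**Working it through.** **Inputs.** Doses lie on a 0.5 mg grid (section 4.5 and the rounding in the tables). The multipliers are 1.25, 0.75 and 0.50 (Appendices 1B, 2A and 2B).

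**Formula.** New dose = floor(2 × k × d) / 2, where d is the current dose in mg and k the multiplier.

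| Current dose (mg) | +25%, before and after rounding | Actual rise | −25%, rounded down | −50%, rounded down |
|---|---|---|---|---|
| 0.5 | 0.625 → 0.5 | 0% | 0 | 0 |
| 1.0 | 1.25 → 1.0 | 0% | 0.5 | 0.5 |
| 1.5 | 1.875 → 1.5 | 0% | 1.0 | 0.5 |
| 2.0 | 2.5 → 2.5 | 25% | 1.5 | 1.0 |
| 2.5 | 3.125 → 3.0 | 20% | 1.5 | 1.0 |
| 3.0 | 3.75 → 3.5 | 17% | 2.0 | 1.5 |
| 3.5 | 4.375 → 4.0 | 14% | 2.5 | 1.5 |
| 4.0 | 5.0 → 5.0 | 25% | 3.0 | 2.0 |

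**Where the limit lies.** On this grid the dose rises only if 0.25 × d is at least 0.5, that is, if d is at least 2.0 mg. Below that, repeating the rule changes nothing.

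**Can patients reach these doses?** The plan's own rules lead there in one step:

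- A 25% cut takes 2.0 mg to 1.5, and 2.5 mg (1.875) to 1.5. The Appendix 2A restart gives the same results.
- A 50% cut takes 2.0 and 2.5 mg to 1.0, and 3.0 and 3.5 mg to 1.5.
- Of the fixed doses in Appendix 1A, 2 mg enters the range by either cut and 3 mg by the 50% cut.
- In the pharmacogenetics arm a low predicted dose could also start there, since no floor is set.

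**Worked case.** A patient on 2.0 mg has an INR of 3.01 to 3.5 and is cut to 1.5 mg. The INR then falls below 1.5. The increase row gives 1.875, rounded down to 1.5 mg. The patient cannot return to 2.0 mg under 1B or 2B.

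**Other readings of the rounding.** If the size of the change were rounded down instead, a quarter of 0.5, 1.0 or 1.5 mg is 0.125, 0.25 or 0.375 mg, and each rounds to 0. The increase still fails at all three doses. The 25% cut would then also do nothing there, and only the 50% cut would lower 1.0 mg (to 0.5) and 1.5 mg (0.75 rounded to 0.5, so to 1.0). The worked case is unchanged, because a quarter of 2.0 mg is exactly 0.5 mg. Rounding the resulting dose is the more natural reading: Appendix 2A speaks of 75% of the dose, and section 4.5 rounds the dose itself.

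**The case against.** The strongest reply is that rounding down is deliberate caution with a drug of narrow therapeutic index. Section 4.5 rounds predicted doses down, and the Background accepts a bias toward under-prediction. The tables also hold the dose at INR 1.51 to 1.99, below the usual target, so a temporary hold during initiation is tolerated at every dose. This explains the direction of rounding. It does not explain a row that orders an increase and never gives one.

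The reply on reach stands. In the traditional arm a patient must first be reduced for an INR above 3 and then fall below 1.5 while still in initiation. For the pharmacogenetics arm the documents give no distribution of predicted doses. Nothing shows that many patients are affected.

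Three stronger readings are tempting, and the documents do not support them:

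- **A maximum length of stall.** A reader might count from the first check ("Check INR if three doses of warfarin had been administered") to the last row of the schedule ("12-14 days after initiation of warfarin"). That row is only an INR check. No date is given for the change to Appendix 3, and section 4.2 ties maintenance dose to repeated in-range INRs on an unchanged dose.
- **Loss of heparin cover caused by the rounding.** The plan says "Once therapeutic INR is achieved, low-molecular heparin should be stopped", and 1B and 2B give no restart rule. That gap exists at every dose and is a separate matter. A patient still below 1.5 at the 2A check continues heparin.
- **A biased primary endpoint.** SAP 7.1 counts titrations performed. An unchanged dose is not one, so no effect on the primary analysis follows.

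**Conclusion.** The point holds as a minor fault in a dosing rule. At 0.5, 1.0 and 1.5 mg the nominal 25% increase is 0% in Appendices 1B, 2A and 2B. That result does not depend on whether the dose or the change is rounded down. The statement that all three doses can still fall rests on rounding the resulting dose. Both statements assume that the tables are followed literally.

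The failure lasts until Appendix 3 applies, for a time that cannot be stated. The number of patients affected is unknown and may be nil.

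**What to change.** In the INR below 1.5 row of Appendices 1B, 2A and 2B, write: *raise by 25%, rounding the result down to a 0.5 mg multiple, and in any case by at least 0.5 mg*. Nothing changes at 2.0 mg and above, where the rule already gives at least one step. The minimum is half of Appendix 3's 1 mg step.

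The investigators should confirm it, because the relative step is large: 0.5/1.5 = 33%, 0.5/1.0 = 50% and 0.5/0.5 = 100%.

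The cost is one line in three tables and a protocol amendment. Each minimum step is a real dose change and adds one counted titration where there is now none, so the date of the change should be recorded if patients are already enrolled. If dosing is complete, the tables need no change. An optional table by arm of INR results below 1.5 that led to no dose change, at doses of 1.5 mg or less, would show whether the fault ever mattered. Section 4.3 already collects the INR values and dose adjustments for it.

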Appendix 3.

Warfarin Dosing Algorithm for ACC Harmonised Clinic during maintenance phase

If INR < 2 or >3, venous INR should be obtained as the correct INR value

INR	ACTION		
< 1.5	Increase dosage by 1mg / dose; repeat blood test for INR in 7 days NB. If patient has prosthetic heart valve, inform doctor-in-charge immediately*		
1.5-1.9	Increase dosage by 0.5mg / dose; repeat blood test for INR in 7 - 10 days		
2.0-3.0	No change		
3.1-3.4	 No bleeding : Repeat INR within 2 weeks if INR is in range on same dose previously for more than 6 months and patient does not have obvious bleeding risks, otherwise: Decrease dose by 0.5mg 		
3.5-4.0	No bleeding: decrease dosage by 0.5mg / dose; repeat blood test for INR in 7 days		
4.1-5.0	Bleeding: inform doctor-in-charge of patient immediately* No bleeding: stop warfarin for 2 days; decrease dosage by 1mg / dose; repeat blood test for INR in 5 - 7 days Bleeding: inform doctor-in-charge of patient immediately*		
5.1-5.5	No bleeding: stop warfarin for 3 days; repeat blood test for INR in 3-5 days; restart warfarin if INR is in therapeutic range (decrease dosage by 1.5mg); Bleeding: inform doctor-in-charge immediately*		
> 5.5	Stop warfarin; inform doctor-in-charge immediately*		

Guideline for Follow-up Visits

INR	Variation	Assessment Date
Out of range	-	3-10 days
(refer to Appendix 3-		
Warfarin Dosing		
Algorithm)		
Within target range	≥ 0.8 units	4-6 weeks
	< 0.8 units	3 months

NB. A repeat blood test should be performed 1 week to 10 days later for all NEW patients (i.e. first-timers) to check the INR so that the dose may be confirmed, even if the initial INR after discharge is within target range.

Appendix 4 Statistical Analysis Plan
